3.5.7 Survival Follow-up – Patients who have disease progression

Once a patient experiences confirmed disease progression or starts a new anti-cancer therapy, the patient moves into the survival follow-up phase and should be contacted by telephone every 12 weeks to assess for survival status until death, withdrawal of consent, or the end of the study, whichever occurs first. If a patient progresses on treatment they will also be required to attend a SFU at 12 weeks or before the initiation of a new anti-cancer treatment; whichever comes first.

3.6 Study Termination

The end of the study is defined when the last patient has completed post-safety follow-up phase (A)/(B) or discontinued the study for other reasons.

3.6.1 Clinical Criteria for Early Trial Termination

Early trial termination will be the result of the criteria specified below:

1. Quality or quantity of data recording is inaccurate or incomplete
2. Poor adherence to protocol and regulatory requirements
3. Incidence or severity of adverse drug reaction in this or other studies indicates a potential health hazard to patients
4. Plans to modify or discontinue the development of the study drug
5. MTD is seen at dose level 1

In accordance with the conditions of supply agreement with Merck ample notification will be provided to the sponsor and sites should alterations to the drug supply change. This is to allow time for appropriate adjustments to be made in regards to the patient's treatment.

3.7 Treatment after Study Termination

Following participation in the study patient care will be decided by the local doctor according to local practise.

4.0 PATIENT SELECTION AND ENROLMENT

4.1 Screening and Enrolment

Principal Investigators (PIs) should keep a record of all patients screened for entry into this study. Copies of the screening logs should be filed in the Site File. For each patient the primary reason for exclusion should be recorded. Diagnostic data obtained as part of the patient's standard care can be used to determine eligibility provided they fall within the protocol defined timelines. Written informed consent must be obtained prior to the patient undergoing any study specific procedures.

4.2 Registration

When the patient signs the consent form they will be allocated a trial identification number that will be used to identify the patient throughout the trial. Once all the screening assessments have been completed and the data entered on the CRFs; the patient will be assessed for eligibility. If eligible the patient will begin on the trial. If the patient is not eligible then the local investigator will make alternative arrangements for the treatment of the patient.

The trial ID will be a unique number that once assigned will become the permanent study identifier for that patient. In the event a patient is registered onto the study but does not begin treatment, then that patient's trial ID will not be reassigned. Treatment will begin within 3 days from the date eligibility has been confirmed. To ensure patient confidentiality patients will only be identified on CRFs, other trial specific forms and all communication to RM-CTU using their assigned trial ID. It is the PI's responsibility to maintain a confidential record of the identity i.e. full name and hospital number for the patients enrolled in this study and their assigned trial ID and date of birth. At the end of the study this record should be archived along with the Site File.

4.3 Stratification

Patients will be stratified in to each arm according to the HPV status of their tumour.

4.4 Patient Replacement Strategy

Additional patients may be enrolled in a given cohort to ensure that the required number of evaluable patients in each cohort is achieved. A patient that discontinues the trial for progressive disease or a drug-related AE will not be replaced. Patients receiving at least one radiotherapy fraction and one dose of pembrolizumab will also be counted in the evaluable population for the primary endpoint of treatment-related toxicity of patients for the respective cohort.

Patients found to be ineligible during screening or do not continue onto treatment or do not reach the visit 6 weeks post chemoradiotherapy can be replaced by new patients in that cohort to ensure there is a minimum of 3 (or 6 if required) patients in each cohort.

All other patients will be assessed for toxicity and secondary endpoints.

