3.0 STUDY DESIGN

3.1 Overall Study Design

This will be a single centre phase 1 dose-escalation study to confirm the safety of combining pembrolizumab with standard platin-based chemoradiotherapy in patients with stage IV high- and intermediate-risk locally-advanced head and neck cancer.

advanced squamous cell carcinoma of the head and neck (LA-SCCHN). 6-36 patients (18 HPV+ve and 18 HPV-ve) will be recruited in a standard 3+3 dose-escalation trial design with an expansion cohort at the maximum tolerated dose (or 200 mg, if no DLT is defined). A pre-loading dose of 100 or 200mg (dependent on dosing level) of pembrolizumab will be given once the patient has completed the screening period. Patients will then return 2 weeks later to begin cycle 1 of a regimen of pembrolizumab 3 weekly at a dose of 100 or 200mg (dependent on dosing level) for a total of 7 cycles (3 during chemoradiotherapy and 4 after chemoradiotherapy).

Parallel studies in HPV-ve and HPV +ve disease will be conducted (note these patients may have different patterns of co-morbidity and, hence, different treatment-related toxicities). The primary endpoint of the study will be safety and tolerability. Dose-limiting acute toxicity will be assessed during administration of study drug according to CTCAEv4.0. The maximum tolerated dose of study drug (or 200 mg in the absence of DLT) will be used in a subsequent randomised phase 2 study comparing standard-of-care therapy with standard-of-care therapy plus study drug.

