3.3 Dose Levels

This study has 2 dosing levels. The rate of entry and escalation to the next dose level will depend upon assessment of the toxicity profile of patients entered at the previous level. Toxicity and assessment for DLT period will be assessed during treatment and up until 6 weeks after the completion of chemoradiotherapy. The DLTs for this study will be defined as: Grade 4 thrombocytopenia (or Grade 3 with haemorrhage); Grade 4 neutropenia lasting >7 days (or Grade 3 with fever); Grade 4 anemia; Grade 4 mucositis (or Grade 3 with confluent lesions lasting >6 weeks after the end of radiotherapy); >2 weeks toxicity-related treatment delay; or any other \geq Grade 3 non-hematologic toxicity (except nausea and vomiting) which in the opinion of the investigator is considered dose-limiting. The results of each dosing level will be reviewed by the safety review committee (SRC) before recruitment to the next dose level can begin.

Escalation to the next dose level will not proceed until the following criteria are satisfied:

- **If 0/3 patients** experience any of the above mentioned DLT's escalation to the next dose level can proceed.
- **If 1/3 patients** experiences any of the above mentioned DLT's the dose level will be expanded to a total of 6 patients.
 - If 1/6 patients experience any of the above mentioned DLT's then escalation to the next dose level can proceed.
 - If \geq 2/6 patients in a specific dose level experience any of the above mentioned DLT's the maximum tolerated dose will have been reached and all subsequent patients will be recruited at the previous dose level.
- **If 2/3 patients** experience any of the above mentioned DLT's then the maximum tolerated dose will have been reached and the expansion cohort phase will begin at the previous dose level. If the MTD is reached at dose level 1 the study will be stopped.

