12.1.4 Dose-Limiting Toxicity of Chemoradiotherapy

The definition of DLT will follow the generally accepted parameters in published phase I trials and will aim to identify any amplification of the expected toxicities of standard chemoradiotherapy by addition of pembrolizumab. The DLT period will be up until 6 weeks after the end of chemoradiotherapy. Therefore, DLT will be defined as: Grade 4 thrombocytopenia (or Grade 3 with haemorrhage); Grade 4 neutropenia lasting >7 days (or Grade 3 with fever); Grade 4 anaemia; Grade 4 mucositis (or Grade 3 with confluent lesions lasting >6 weeks after the end of radiotherapy); >2 weeks toxicity-related treatment delay; or any other ≥Grade 3 non-hematologic toxicity (except nausea and vomiting) which in the opinion of the investigator is considered dose-limiting.

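### The DLT window closes before one of its own criteria can be met, and section 4.4 does not tie the 3 or 6 patients in the escalation rules to a completed window

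*Combined protocol and SAP*

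**What the plan says.** **The window.** Section 3.3: "Toxicity and assessment for DLT period will be assessed during treatment and up until 6 weeks after the completion of chemoradiotherapy". Section 12.1.4: "The DLT period will be up until 6 weeks after the end of chemoradiotherapy". Both sections list among the DLTs Grade 4 mucositis or "Grade 3 with confluent lesions lasting >6 weeks after the end of radiotherapy". The overview in section 3.1 describes the period differently: "Dose-limiting acute toxicity will be assessed during administration of study drug according to CTCAEv4.0".

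**Who counts.** Section 4.4 makes four relevant statements:
- On leaving early: "A patient that discontinues the trial for progressive disease or a drug-related AE will not be replaced".
- Patients with at least "one radiotherapy fraction and one dose of pembrolizumab will also be counted in the evaluable population for the primary endpoint of treatment-related toxicity".
- Patients who "do not reach the visit 6 weeks post chemoradiotherapy can be replaced by new patients in that cohort", and this is done "to ensure there is a minimum of 3 (or 6 if required) patients in each cohort".
- All other patients are assessed for toxicity and the secondary endpoints.

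**What the count decides.** Under sections 3.2 and 3.3, 0/3 or 1/6 DLTs allows escalation, 1/3 expands the cohort to 6, and 2/3 or at least 2/6 stops escalation. The rules apply separately in each HPV cohort. Section 8 does not define a DLT-evaluable set; 8.2.5 says only that DLTs are summarised as overall frequencies.

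**The concern.** A 3+3 rule is only as good as its numerator and denominator. Each patient in the 3 or 6 should either have had a DLT or have been watched for the whole DLT period without one. Section 4.4 does not require this. Its evaluable set has no follow-up condition, its bar on replacement depends on the reason for leaving rather than on DLT status or completeness of observation, and it is silent on whether a replaced patient's DLT is retained. The window has a separate problem: one of the listed criteria cannot be fulfilled until the window in 3.3 and 12.1.4 has closed. Section 1.2.3 names mucosal toxicity as one of the primary acute toxicities of interest, so the affected criterion is not marginal. With cohorts of 3 or 6, one misclassified patient can change an escalation decision and the resulting MTD.

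**Working it through.** **1. The plan's own figure.** Section 8.2.4 gives 6 to 36 patients. Minimum: 3 × 2 HPV cohorts = 6. Maximum: (6 × 2 dose levels + 6 expansion) × 2 cohorts = 36. Both reproduce. The plan states no target DLT rate and no operating characteristics.

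**2. The calendar with no delays.** The pre-loading dose is 2 weeks before cycle 1 (3.2), cycle 1 is week 0, and radiotherapy runs 7 weeks (Trial Summary).
- End of chemoradiotherapy: week 7. End of the DLT period in 3.3 and 12.1.4: 7 + 6 = week 13.
- Grade 3 confluent mucositis lasting more than 6 weeks after radiotherapy is met only after week 13, so after that period closes.
- Under 3.1, the period would run to the last pembrolizumab dose, 6 × 3 = week 18. The mucositis criterion could then be scored.
- The visit in 4.4 falls at week 13. Table 2 as available has weeks 12 and 15, which are 5 and 8 weeks after chemoradiotherapy (days 35 and 56). The ±3 days that 6.3.7 allows for dosing (days 32–38 and 53–59) do not reach day 42.

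**3. Readings of the denominator in 4.4.**

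| Reading | Who fills the 3 or 6 | Effect on the DLT count |
|---|---|---|
| A | Anyone with one fraction and one dose | A partly observed patient can be scored DLT-free; the count may be understated |
| B | Patients who reach the 6-week visit; others may be replaced | If a replaced patient's DLT is not carried over, it is lost; progression drop-outs are not replaced although their window is incomplete |
| C | Treated patients stay, and replacements are added to reach the minimum | Not lowered, but one added patient makes 3 + 1 = 4 or 6 + 1 = 7, and 3.3 has rules only for 3 and 6 |

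**4. Illustration of reading A.** The documents give no DLT rate, so p is assumed. A dose is cleared with 0/3, or with 1/3 followed by 0 in the next 3:

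P(clear) = (1−p)³ + 3p(1−p)² × (1−p)³

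At p = 0.33: 0.3008 + 0.4444 × 0.3008 = 0.434.

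Now let one of the first three leave just after the first fraction and be scored DLT-free. The window, counted from the pre-loading dose, is 2 + 7 + 6 = 15 weeks, of which about 2 are observed. With DLT risk assumed even over the window, that patient's chance of an observed DLT is p₁ = p × 2/15 = 0.044.
- P(0/3) = 0.67² × 0.956 = 0.4291
- P(1/3) = 2 × 0.33 × 0.67 × 0.956 + 0.67² × 0.044 = 0.4425
- P(clear) = 0.4291 + 0.4425 × 0.3008 = 0.562

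The same formulas at other assumed rates:

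| Assumed p | Full observation | p₁ | P(0/3) | P(1/3) | (1−p)³ | One patient seen for 2 of 15 weeks |
|---|---|---|---|---|---|---|
| 0.20 | 0.709 | 0.0267 | 0.6229 | 0.3285 | 0.512 | 0.791 |
| 0.33 | 0.434 | 0.044 | 0.4291 | 0.4425 | 0.3008 | 0.562 |
| 0.40 | 0.309 | 0.0533 | 0.3408 | 0.4736 | 0.216 | 0.443 |

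I give no figure for reading B or for the mucositis criterion. Each would need a rate (DLT patients replaced, or prolonged Grade 3 mucositis) that the documents do not supply.

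**The case against.** The best defence is reading C. Section 4.4 says such patients are *also* counted for the primary endpoint and speaks of a *minimum* of 3 or 6; no passage provides for deleting a DLT, and 3.3 counts patients who experience one. On that reading nothing is understated. This stands as a legitimate reading, and it is why a low bias cannot be asserted. It does not settle the matter, because it produces cohorts for which 3.3 has no rule.

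Several provisions also limit the damage:
- AEs are recorded to the 12-week safety visit (5.3.1), so long non-observation mainly needs withdrawal, loss to follow-up or early new therapy.
- Patients leaving for a drug-related AE are not replaced, and 4.4 does not confine that to pembrolizumab.
- A patient who misses the 6-week visit can be replaced, so the case in step 4 need not arise; but replacement is optional, and barred after progression.
- Progression drop-outs inside the window should be few, since the first on-study scan is at week 15.
- Other non-haematological toxicity of Grade 3 or above can be called a DLT by the investigator.
- A safety review committee makes the escalation decisions (10.8.2).

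All of this stands. It makes a miscount less likely but does not define the denominator.

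On the window, 3.3 and 12.1.4 are the operative definitions, and 3.1 is an overview sentence. Its conflict is the lesser one and would lengthen the window, so it does not support an argument for undercounting. The mucositis mismatch concerns one sub-criterion at the boundary of the window, but it is in the text of both defining sections.

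The figure after section 3.2, the flow chart in 3.4 and the committee charter are not available to us, and any of them might answer part of this.

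**Conclusion.** The point holds as an ambiguity that should be fixed. The DLT period in 3.3 and 12.1.4 ends before one listed criterion can be met on the planned schedule; the 6-week visit is not in Table 2 as available; and 4.4 does not link the 3 or 6 to completion of the window. Some readings would understate the DLT count, and one would not.

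A reader might infer that the trial's DLT count *is* biased low, or that escalation is unsafe. The documents do not support that: the direction depends on the reading, and no drop-out or DLT rate is given. A reader might also put an assumed share of early leavers, such as 10–30%, into the formulas and take the result as the size of the bias; that would be pure assumption.

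The shift from 43% to 56% shows only how much one misclassified patient can matter. It rests on an assumed 33% DLT rate, DLT risk spread evenly over 15 weeks, one of the first three patients leaving at the first fraction, and that patient being neither replaced nor excluded. If drop-out is unrelated to toxicity and drop-outs are excluded and replaced, there is no bias; the text does not require that handling. My confidence is medium.

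**What to change.** In 3.3, 4.4 and 12.1.4, and consistently in 3.1, define one DLT-evaluable set for the escalation decision:
- A patient with a protocol-defined DLT at any time in the window after the first pembrolizumab dose always counts and is never removed by replacement.
- A patient without a DLT counts only if the DLT window is completed. Otherwise the patient does not fill a slot and may be replaced, for the escalation decision only. The sponsor should reconcile this with the present sentence against replacing patients who progress.
- The 3.3 rules apply to this set. The one-fraction/one-dose set is kept for the toxicity tables.

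Reconcile the DLT window with the mucositis criterion and with a visit that is in the schedule; how to do so is for the sponsor to decide.

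The cost is protocol wording, possibly a few replacement patients beyond the stated maximum of 18 per cohort (36 in total), and a slightly later escalation decision. Section 8.2.4 should then state its numbers as evaluable patients.

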6.10 Withdrawal from the Study

Patients have the right to discontinue study treatment any time for any reason, without prejudice to their medical care. Withdrawal from the study refers to discontinuation of both study medication and study assessments; this can occur at any time according to the following reasons:

- Patient decision
- Lost to follow-up
- Death
- PI decision

Patients may withdraw consent at any time for any reason or be dropped from the trial at the discretion of the investigator should any untoward effect occur. In addition, a patient may be withdrawn by the investigator or the Sponsor if enrolment into the trial is inappropriate, the trial plan is violated, or for administrative and/or other safety reasons. When a patient discontinues/withdraws prior to trial completion, all applicable activities scheduled for the final trial visit should be performed at the time of discontinuation, these are listed in the schedule of study assessment (Table 2). Any adverse events which are present at that time should be followed in accordance with the safety requirements outlined in Section 7.

Patients who a) attain a CR or b) complete 24 months of treatment with pembrolizumab may discontinue treatment with the option of restarting treatment if they meet the criteria. After discontinuing treatment following assessment of CR, these patients should return to the site for post-treatment follow-up visits and/or 12 weeks safety follow-up visit and then proceed to the follow-up period of the study.

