8.2.5 Data analysis

All quantitative data will be presented as number of observations, means and SDs for normally distributed data or as median and interquartile ranges for data that appear to be non-normally distributed. Qualitative data will be presented as number of observations and frequencies. When appropriate, data will be presented together with 95% confidence intervals. All statistical tests will be two-tailed and a p-value <0.05 (5%) will be considered as achieving statistical significance. The analysis will be performed separately in HPV-ve and HPV+ve cohorts, respectively.

- Baseline characteristics will be summarized using descriptive statistics. Dose limiting toxicity will be summarized using overall frequencies. Incidence (highest grade) of side effects of radiotherapy (CTCAE scale v 4.0, for acute side effects and LENT SOMA for late radiotherapy scoring systems) will be reported.
- Duration of clinical benefit will be calculated as the number of patients who had a best overall response of CR, PR, or SD according to the RECIST criteria until the first date of recurrence or progressive disease (PD) and will be measured at the landmark points in the study **6 months, 1 year and 2 years, respectively**. They will be presented as proportions and 95% confidence intervals will be reported if appropriate.
- Progression free and overall survival will be determined using Kaplan-Meier methods **presenting the median survival times, and survival rates will be reported at 6 months, 1 and 2 years, respectively**. Overall survival will be measured from date of treatment to date of death from any cause; surviving patients will be censored at date last known to be alive. Progression free survival will be measured from start of treatment to date of first appearance of disease progression, relapse or death from any cause. Patients alive without progression or relapse will be censored at date last known to be alive. Survival curves will be estimated for each HPV cohort and compared using the log-rank test.

- The levels of CD4, CD8, T regulatory cell (CD4/CD25, FOXP3), B cells, NK cells and Circulating free tumour DNA pre RT, during RT and post RT will be presented as descriptive statistics according to their HPV status. The expression of PD1 (and other immune exhaustion markers) on immune cells and PDL1 on tumour cells will be presented as descriptive statistics.

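### Read literally, the last sentence of Section 4.4 leaves some treated patients who die early out of PFS, OS and clinical benefit, and Section 8.2.5 names no analysis set to prevent it

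*Combined protocol and SAP*

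**What the plan says.** Section 4.4 (Patient Replacement Strategy) makes four statements that bear on this point.

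- Exemption from replacement: "A patient that discontinues the trial for progressive disease or a drug-related AE will not be replaced".
- Toxicity population: "Patients receiving at least one radiotherapy fraction and one dose of pembrolizumab will also be counted in the evaluable population for the primary endpoint".
- Who may be replaced: patients found ineligible at screening, patients who do not go on to treatment, and patients who "do not reach the visit 6 weeks post chemoradiotherapy can be replaced by new patients in that cohort". The stated purpose is to keep at least 3 (or 6) patients per cohort.
- Then, as the closing sentence: "All other patients will be assessed for toxicity and secondary endpoints".

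Section 8.2.5 (Data analysis) defines the survival endpoints without naming a population. "Overall survival will be measured from date of treatment to date of death from any cause". "Progression free survival will be measured from start of treatment to date of first appearance of disease progression, relapse or death from any cause". Survivors are censored when last known alive. The planned use is: "Survival curves will be estimated for each HPV cohort and compared using the log-rank test".

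In Section 6.10, "Withdrawal from the study refers to discontinuation of both study medication and study assessments", and death is one of the listed reasons.

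**The concern.** Of the three replaceable groups, the first two contain no treated patients. The third can. A patient may have had the pre-loading dose, several pembrolizumab cycles and a full course of chemoradiotherapy, and still die before the six-week visit. The closing sentence of 4.4 follows directly on that list, so the natural reading of its word 'other' is everyone not on the list. No other text says who is assessed for the secondary endpoints.

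Replacement is a device for filling a DLT cohort. If it also decides who is in the survival analysis, membership depends on what happened after treatment began. Some early deaths then disappear from both numerator and denominator, and PFS and OS are partly conditioned on surviving to the visit. The clinical-benefit proportion has the same problem through its denominator. Two analysts could build different survival sets and each cite the protocol.

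**Working it through.** **1. The plan's own figure.** Section 8.2.4 gives 6 to 36 patients. Minimum: 3 × 2 HPV cohorts = 6. Maximum: (6 + 6 + 6) × 2 = 36, or 18 per cohort. Both reproduce. Neither includes any allowance for replaced patients.

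**2. When the visit falls.** Radiotherapy ends at week 7 counted from cycle 1 (Section 8.2.2), and 7 + 6 = week 13. The pre-loading dose is given 2 weeks before cycle 1 (Section 3.1), so the visit is 15 weeks after first treatment. That is 15/26.1 = 57% of the way to the 6-month landmark. Table 2 has clinic visits at weeks 12 and 15 but none at week 13, so the cut-off is not tied to a scheduled visit.

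**3. Who is affected, reading the sentence literally.**

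| Treated patient not reaching the visit because of | Replaceable under 4.4? | Effect on survival estimates |
|---|---|---|
| Discontinuation for progression | No | None; stays in |
| Discontinuation for a drug-related AE | No | None; stays in |
| Withdrawal with no known event | Yes | Little; would be censored early in any case |
| Death from another cause | Yes | A PFS and OS event is lost |

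Only the last row biases the curves materially, and always upward.

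**4. Effect of one such death.** Suppose n patients are retained, all alive at 6 months, and k further treated patients died early and were left out. The literal reading gives n/n = 100%. The all-treated figure is n/(n + k).

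- n = 18 (cohort maximum): k = 1, 18/19 = 94.7%; k = 2, 18/20 = 90.0%; k = 3, 18/21 = 85.7%.
- n = 12 (3 + 3 + 6, the shortest route through both dose levels and the expansion): k = 1, 12/13 = 92.3%.

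The shift is therefore 5.3 to 7.7 points for one patient. With n = 18 and 4 later deaths by 1 year, it is 14/18 = 77.8% against 14/19 = 73.7% for k = 1.

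**5. How likely early deaths are (assumption, upper bound).** Section 1.1 quotes 3-year OS after concurrent chemoradiotherapy in oropharynx cancer: 46.2% (high risk) and 70.8% (intermediate risk). Assume a constant hazard h = −ln(S₃)/3, giving 0.2574 and 0.1151 per year. Death before the visit has probability p = 1 − exp(−h·t₀), with t₀ = 13/52 to 15/52 years. The chance of at least one in 18 is 1 − (1 − p)¹⁸. If every early death were dropped, 1-year OS would read exp(−h(1 − t₀)).

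| | High risk | Intermediate risk |
|---|---|---|
| p | 6.2–7.2% | 2.8–3.3% |
| At least one death in 18 | 69–74% | 40–45% |
| 1-year OS, all treated | 77.3% | 89.1% |
| 1-year OS, all early deaths dropped | 82.4–83.3% | 91.7–92.1% |
| 1-year OS, half dropped | 79.8–80.2% | 90.4–90.6% |

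These counts include deaths from every cause, whereas 4.4 keeps patients who discontinue for progression or a drug-related AE. The true effect is smaller than the all-dropped row; the documents do not allow it to be fixed more closely.

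**The case against.** The strongest reply is that this is loose drafting and not a rule. The closing sentence does not say that only the other patients are assessed. Read literally, it would also remove the third group from toxicity, against the rule a paragraph earlier in the same section, which suggests the authors did not intend an exclusion. Section 8.2.5 excludes nobody, and Sections 3.5.6 and 6.9.1 keep following patients who stop without progression, which fits an all-treated analysis. Replacement is optional, and a patient who stops treatment can still attend the visit. The numbers are also small against the noise: the exact 95% interval is 81.5–100% for 18/18 and 73.5–100% for 12/12.

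Most of this stands, and it limits the size of the point. It does not remove it. Continued follow-up means the data may exist; it does not say whose data enter the curves. A contradiction inside 4.4 is itself a reason to correct the text. Imprecision does not excuse an avoidable bias with a known direction.

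Three stronger readings are tempting but not supported:

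- That every treated patient who leaves before week 13 vanishes from survival. The exemption keeps discontinuations for progression and drug-related AEs, and withdrawals with no known event barely move a Kaplan-Meier curve.
- That stopping for platin or radiotherapy toxicity is plainly replaceable. Section 4.4 does not define which drug it means. Section 7.3.2 ties causality to the investigational product, but a platin is also a drug, so this is open.
- That inflated PFS and OS will feed the randomised phase 2 trial. Section 3.1 carries forward only the dose.

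**Conclusion.** The point holds in limited form. The only text on who is assessed for the secondary endpoints, followed as written, leaves out treated patients who die before about week 13 of causes other than progression or a drug-related AE. It cannot be squared with a survival endpoint that starts at treatment and counts any death, nor with the toxicity-evaluable rule in the same section.

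The bias is upward and confined to a small group. The shift of 5.3 to 7.7 points in 6-month OS is illustrative: it assumes exactly one such death, left out, with all 18 or 12 retained patients alive at 6 months. The constant-hazard figures are an upper bound resting on historical oropharynx data. Severity is moderate: the survival consequence falls on secondary endpoints, and nothing here shows that dose escalation is affected.

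**What to change.** - In 8.2.5, add one sentence: PFS, OS and clinical benefit are analysed in all patients who received at least one dose of trial treatment, whether or not they were replaced.
- In 4.4, replace the closing sentence with one saying that replacement affects only the DLT-evaluable set and that replaced patients who were treated remain in the toxicity and secondary analyses. Word it so that it agrees with the fraction-plus-dose rule for toxicity earlier in the section.

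While editing, it would help to note in 8.2.4 that replacements can take the total above 36.

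The cost is two sentences, with no change to treatment or visits. Survival figures may be slightly less favourable. If an all-treated analysis was always intended, the results do not change.
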